9.2.4.2 Adverse Events

Adverse events are clinically unfavorable or unintended signs (including clinically significant abnormal test values), symptoms, or diseases observed after administration of investigational product during the safety evaluation period, whether or not considered related to investigational product.

The investigator (subinvestigator) will investigate adverse events that occur in subjects from the start of administration of investigational product to the evaluation day 3 months after onset and record them in the case report form.

(1) Symptoms or Diseases

The investigator or subinvestigator will confirm the presence or absence of adverse events by interview and medical examination.

(2) Objective findings

Any clinically significant abnormality determined by the Investigator (or Subinvestigator) as * will be handled as an adverse event.

* "Clinically significant abnormalities" will be assessed according to the following criteria.

- If related to clinical signs or symptoms

However, if the symptom or sign has been separately reported as an adverse event, it is not necessary to regard the test abnormality as an adverse event.

- Medical or surgical intervention was performed for the abnormal test value.
- The administration method of investigational product is changed (Dose modification, suspension, discontinuation, etc.) due to the abnormal test value.
- Other clinically significant abnormalities as determined by the Investigator (or Subinvestigator)

(3) Adverse Event Assessment and Criteria

1) Start Date

The start date is defined as the date when the symptom is observed or the test date when the laboratory test abnormality is observed.

2) Severity

The severity of adverse events will be classified according to the following criteria:.

1. Mild: The event does not affect the subject's daily life.
2. Moderate: The event interferes with the subject's daily life to some extent.
3. Severe: The degree to which the event interferes with the subject's daily life.

3) Seriousness

The seriousness of adverse events will be classified as follows:.

1. Non-serious: Other than 2
2. Serious: a) to f) below
 - a) Results in death
 - b) Is life-threatening (The term "life-threatening" in the definition of "serious" refers to an event/reaction in which the patient was at risk of death at the time of the event/reaction; it does not refer to an event/reaction which hypothetically might have caused death if it were more severe,.)
 - c) Requires inpatient hospitalization or prolongation of existing hospitalization (Excluding admission for administrative or social reasons or for convenience of the subject)
 - d) Results in persistent or significant disability/incapacity (substantial disruption of the ability to conduct normal life functions)
 - e) Is a congenital anomaly/birth defect
 - f) is a medically important event or reaction (Medical and scientific judgment should be exercised in deciding whether other situations should be considered serious reactions, such as important medical events that might not be immediately life-threatening or result in death or hospitalisation but might jeopardise the patient or might require intervention to prevent one of the other outcomes listed in the definition above. Examples of such events are intensive treatment in an emergency room or at home for allergic bronchospasm, blood dyscrasias or convulsions that do not result in hospitalization or development of dependency or abuse.).

4) Relationship to investigational product

The investigator will assess whether there is a "reasonable possibility" that investigational product may have caused the adverse event. The evaluation will be determined in consideration of causes other than investigational product such as the natural course of the underlying disease including the primary disease and complications, concomitant therapies, and other risk factors, as well as the temporal relationship between administration of investigational product and the onset of the event (Recurrence after readministration, disappearance after discontinuation, etc.). Adverse events for which a causal relationship with investigational product is assessed as "reasonable possibility" will be regarded as adverse drug reactions.

1. Reasonable possibility
2. No reasonable possibility

5) Outcome

The outcome of an adverse event is classified into the following 6 levels.

1. Recovered/Resolved
2. Recovering/Resolving
3. Not recovered/not resolved
4. Recovered/resolved with sequelae
5. Death
6. Unknown

6) Date of outcome

The date of outcome will be classified according to the following criteria.

Recovered/Resolved: Date of recovery. However, if the date of recovery cannot be identified, it will be the date when the outcome is confirmed or determined.

Recovering/Resolving: Date on which remission was confirmed or determined

[figure not shown]
Not recovered/not resolved: Date of confirmation or determination of "not recovered"

Recovered/resolved with sequelae: Date when sequelae are confirmed or determined

Death: Date of death. However, if the date of death cannot be identified, it will be the date when death is confirmed or determined.

Unknown: Date of death if the outcome is unknown because the subject died from a cause other than the adverse event. For others, it is the date of confirmation or judgment.

7) Follow-up

- The safety evaluation period will be from the start date of treatment with investigational product to the end date of the observation period (the date when all specified 3-month evaluations are completed), and the presence or absence of adverse events will be investigated.

- The duration of the period (2) after the end of the observation period will be 14 days, and adverse events occurring during the safety evaluation period (treatment period with investigational product + (1)) will be followed up.
- The course of adverse events followed up during the period (2) after the end of the observation period should be recorded in the case report form.
- If an adverse event is resolving or not resolved, the date of outcome in the CRF should be the last day of observation during the period specified in (2).
- (2) For ADRs whose outcome is "recovering/resolving" or "not recovered/not resolved" at the end of the period specified in, the subsequent clinical course ((3)) will be investigated.
- If there is a valid reason for termination of the investigation after the end of the safety evaluation period (after the end of (1)), the reason will be recorded in the source documents, etc. and the follow-up investigation will be terminated.

(4) Items to be recorded in the case report form

If any adverse event is observed, the investigator (subinvestigator) will record the name of the adverse event *, date of onset, severity, seriousness, causal relationship with investigational product, details of treatment given (Drugs, therapies, etc.), outcome, and date of outcome in the adverse event section of the case report form. If the follow-up investigation is judged unnecessary because the outcome of an adverse event is "recovered/resolved" or "recovered/resolved with sequelae" or "death," the reason should be recorded in the source document, etc. If the causal relationship with investigational product is "no reasonable possibility," the reason for the judgment will be recorded in the source document, etc.

- * "Adverse event term" should be based on the following criteria:
 - In principle, a diagnosis should be used.
 - If the diagnosis is unclear, the symptom should be used.
 - If multiple symptoms are present and can be described by a single diagnosis, the diagnosis should be used.
 - Surgical procedures, etc. are not regarded as adverse events. If a disease or symptom requiring surgical procedures, etc. is confirmed, it will be regarded as an adverse event.

9.2.5 Blood sampling for gene analysis

Blood sampling will be performed once at any time point from the start of investigational product to the evaluation day 3 months after the onset. The volume of blood to be collected will be approximately 8.5 mL (See "25. Genetic analysis test" for details.).

10. Evaluation method and criteria

10.1 Efficacy

10.1.1 NIHSS

The NIHSS is a scale to objectively evaluate neurological symptoms of cerebral infarction and consists of 15 items: level of consciousness, disturbance of consciousness (Questioning, obedience), best gaze, visual field, facial paralysis, upper limb movements (right and left), lower limb movements (right and left), ataxia, sensation, best language, dysarthria, decreased extinction, and disturbance in attention. The total raw score of each item is 0~42 points, but if ataxia cannot be

performed, it is judged to be 0 points, and therefore the most severe case receives 40 points.

(See "5.4.1 Efficacy Endpoints," "9.2.3 Efficacy Endpoints," and "Attachment 1 NIHSS. ")

10.1.2 mRS

The mRS will evaluate the severity of sequelae after the onset of cerebral infarction on a 7-point scale from Grade 0 "No symptoms at all" to Grade 5 "Severe disorder" plus Grade 6 "Death."

(See "5.4.1 Efficacy Endpoints," "9.2.3 Efficacy Endpoints," "Attachment 2: Questionnaire for mRS," and "Attachment 3: Assessment Criteria for mRS. ")

10.1.3 BI

BI is a scale which evaluates 10 items of ADL (Feeding, transfer from wheelchair to bed, dressing, toileting, bathing, walking, going up and down stairs, dressing, bowel control, urinary control) with 5 points for each item, and the total score is 0~100 points.

(See "5.4.1 Efficacy Endpoints," "9.2.3 Efficacy Endpoints," and "Attachment 4 BI. ")

10.1.4 FIM

The FIM assesses 13 motor items and 5 cognitive items on a 7-point scale consisting of 1~7 items each. The motor items are divided into four major categories: self-care, excretion control, transfer, and movement. The total score is 18~126 points.

(See "5.4.1 Efficacy Endpoints," "9.2.3 Efficacy Endpoints," and "Attachment 5 FIM. ")

[REDACTED]

[REDACTED]

[REDACTED]

[REDACTED]

(See "5.4.1 Efficacy Endpoints," "9.2.3 Efficacy Endpoints," and " [REDACTED] ")

10.1.6 Brain imaging

Infarct lesion volume, degree of cerebral edema, and presence or absence of intracranial hemorrhage will be evaluated by the Image Evaluation Committee as follows.

Infarct volume will be measured on pre-dose DWI and 3-month FLAIR images.

Change in edema will be measured from the DWI findings on Day4 and Day14.

Presence/absence and severity of bleeding will be determined from T2*WI findings on Day4 and Day14.

The details will be specified in a separate written procedure.

10.2 Safety

10.2.1 Adverse events and adverse drug reactions (see "9.2.4.2 Adverse events" for details)

10.2.2 Neurological examination (see "9.2.4.1 Objective findings, (4) Neurological examination" for details)

11. Toxicity Management

[figure not shown]
11.1 Handling of serious adverse events

If any serious adverse event occurs during the period from the start of treatment with investigational product until the day of evaluation 3 months after the onset, the investigator (subinvestigator) will immediately provide appropriate treatment to the subject, regardless of the causal relationship with investigational product.

When an SAE occurs, the investigator or subinvestigator must immediately report it to the monitor (in writing in principle), and provide detailed information in writing to the sponsor within 7 days after the report. The investigator will also report the above SAE to the head of the study site.

The relationship between the definitions of serious adverse events shown in (PAB Notification No. 227 issued by the Director of the Evaluation and Licensing Division, ICH "Serious" criteria) and "Article 273 of the Regulation for Enforcement of the Act on Securing Quality, Efficacy and Safety of Products Including Pharmaceuticals and Medical Devices" in "9.2.4.2 Adverse events" is as follows.

[Definition of serious adverse events]

11.2 Significant Adverse Events

For the purpose of examining the safety profile, AEs of special interest are defined as follows.

- (1) Renal disorder
Serum creatinine >2.0 mg/dL
- (2) Drug-induced liver injury
¹⁹ if all of the following definitions of Hy's law are met:
 - a) AST or ALT $> 3 \times$ ULN
 - b) Total bilirubin > 2 times the upper limit of normal
 - c) ALP $< 2 \times$ ULN
 - d) There is no explanation for the above laboratory abnormalities a), b), and c) other than investigational product.
- (3) Neurological disorders (medically significant changes on neurological examination in the healthy side)

If such an adverse event occurs, the investigator must inform the monitor immediately about the situation. The monitor will confirm with the investigator (subinvestigator) whether or not the study can be continued.

For significant adverse events, the sponsor will appropriately evaluate the occurrence status and frequency, and examine the appropriateness of study continuation and the necessity of protocol amendment.

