j) Only white blood cell count (WBC), red blood cell count (RBC), hemoglobin (Hb), hematocrit (Ht), platelets (Plt), AST (GOT), ALT (GPT), LDH, ALP, γ -GTP, total bilirubin (T-Bil), CK (CPK), urea nitrogen (BUN), serum creatinine (Cre), and eGFR will be examined urgently in the hospital to confirm the eligibility as a case.

k) Only red blood cell (RBC), platelet (Plt), AST (GOT), ALT (GPT), LDH, ALP, total bilirubin (T-Bil), CK (CPK), urea nitrogen (BUN), and serum creatinine (Cre) will be measured in the hospital every day for 5 days from the start day of treatment to confirm the safety of subjects.

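### Criterion d) makes the immediate liver notice and the sponsor's liver count depend on excluding every other cause, unlike the renal criterion

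*Protocol*

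**What the plan says.** Protocol section 11.2 lists three adverse events of special interest.

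- **Renal.** The whole definition is "Serum creatinine >2.0 mg/dL".
- **Liver.** The event exists "if all of the following definitions of Hy's law are met": a) AST or ALT above 3 times the upper limit of normal, b) total bilirubin above 2 times the upper limit, c) ALP below 2 times the upper limit, and d) "There is no explanation for the above laboratory abnormalities a), b), and c) other than investigational product".
- **Neurological.** Medically significant change on examination of the healthy side.

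Two consequences follow in the same section. For the site: "If such an adverse event occurs, the investigator must inform the monitor immediately about the situation". For the sponsor: "For significant adverse events, the sponsor will appropriately evaluate the occurrence status and frequency", with a view to whether the study should continue or the protocol be amended.

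AST, ALT, ALP and total bilirubin are all in the local safety panel, which under section 9.1 note k "will be measured in the hospital every day for 5 days from the start day of treatment to confirm the safety of subjects". For adverse events in general, section 9.2.4.2 sets a different causality standard: "The investigator will assess whether there is a 'reasonable possibility' that investigational product may have caused the adverse event".

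**The concern.** Items a) to c) can be read from one local blood sample. Item d) is a judgement about cause, and it sits inside the definition that starts an immediate notice. A criterion suited to final classification is therefore also the trigger of an early warning.

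Two things are at stake. The first is speed: a site applying the text has no special-interest event to notify until it has decided that nothing else explains the values. The second is completeness: a subject with the full laboratory pattern and another possible cause drops out of the sponsor's special-interest count, so a liver signal could be under-counted. Alternative causes are foreseeable. Protocol section 1 describes usual care with anti-oedema agents, anticoagulants and antiplatelet agents. Current antibiotic treatment is an exclusion at enrolment (section 3.3), but antibiotics are not in the list of prohibited drugs in section 8.5.1. SAP section 4.1 states that there is no data monitoring board.

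**Working it through.** The plan gives no figure on this point, so there is none to reproduce. The check is mainly a reading of the text, followed by an illustration on assumed rates.

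**Step 1: is d) necessary?** Yes. Section 11.2 joins a) to d) with an all-of condition. Failing d) means there is no liver event under 11.2.

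**Step 2: what hangs on the event?** The immediate notice and the sponsor's frequency review are both conditional on it. Neither has a separate trigger on a) to c), and the available text has no provisional category for a suspected case.

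**Step 3: is this consistent with the rest of the protocol?**

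| Item | Laboratory condition | Causality condition |
|---|---|---|
| Renal event (11.2) | Creatinine threshold | None |
| Liver event (11.2) | a), b), c) | Nothing other than the product explains them |
| Adverse drug reaction (9.2.4.2) | None | Reasonable possibility |

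A liver abnormality can thus be classed as an adverse drug reaction and still fail d).

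**Step 4: do other routes close the gap?**

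- Serious adverse events go to the monitor immediately with no causality condition (11.1). The liver pattern is not listed as serious in 9.2.4.2, so this often rests on a judgement that the event is medically important.
- Clinically significant laboratory abnormalities are recorded as adverse events whatever the cause (9.2.4.2), but without an immediate-notice rule.
- Local Day 1 to Day 5 results go into the case report form. Central results on Day 4, 7, 10, 14, Week 3 and at discharge are retained by the sponsor (9.2.4.1).
- SAP section 7.3.2 specifies summaries, shift tables and a listing for clinically significant findings; its parameter list is the central-laboratory one. SAP section 14.2 has no special-interest table and no table combining AST or ALT, bilirubin and ALP within a subject.

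The data therefore reach the sponsor, but no route assures immediate notice of the combined pattern and no planned table counts it.

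**Step 5: size, as an illustration.** Let N = 336 (planned total, Protocol 6.1), r = rate of subjects meeting a) to c), and q = share of those with another possible explanation. Both r and q are assumptions; the documents give neither.

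- Expected section 11.2 liver notices = N × r × (1 − q)
- P(at least one) = 1 − [1 − r(1 − q)]^N

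Example, r = 0.5% and q = 50%: 336 × 0.005 × 0.5 = 0.84, and 1 − (1 − 0.0025)^336 = 57%.

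| q | r = 0.2% | r = 0.5% | r = 1.0% |
|---|---|---|---|
| 0% (trigger on a to c) | 0.67; 49% | 1.68; 81% | 3.36; 97% |
| 25% | 0.50; 40% | 1.26; 72% | 2.52; 92% |
| 50% | 0.34; 29% | 0.84; 57% | 1.68; 81% |
| 75% | 0.17; 16% | 0.42; 34% | 0.84; 57% |
| 90% | 0.07; 7% | 0.17; 16% | 0.34; 29% |

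Each cell gives expected notices and the probability of at least one. The proportional loss is q whatever N is. The absolute numbers would be smaller in the truncated trial (SAP section 1).

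**The case against.** The item is headed as drug-induced liver injury and adopts a referenced definition (Protocol reference 19), so causality belongs to the event being defined. That is fair for classification. It does not explain why the same definition should govern an immediate notice, when the renal item does not work that way.

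Three stronger readings are tempting, and the documents do not support them.

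- *A reader might infer that no notice can be given until a causality work-up is complete.* Section 11.2 prescribes no work-up and no time for one. An investigator who sees no other explanation when the result arrives can judge d) met and notify at once. Delay is a plausible consequence, not a stated rule.
- *A reader might infer that the notice will rarely be given.* No figure supports a frequency. The treatment description in section 1 is general background. It also names thrombolytics, which the trial prohibits, and it says nothing about liver toxicity. Section 3.3 removes some alternative causes at entry: ALT, AST or γ-GTP above 2.5 times the upper limit, alcohol dependence or drug abuse, and current antibiotic treatment.
- *A reader might infer that this notice is the sponsor's only sight of hepatic events.* The routes in step 4 of the working do not depend on d), and section 16 allows new safety information to prompt a review of continuation.

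Two limits also stand. Part of section 11 and some attachments are not visible, so a provisional step placed there cannot be ruled out. And recruitment has ended with the analysis declared exploratory (SAP sections 1 and 8), which leaves little prospective benefit.

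**Conclusion.** The point holds as a defect in the reporting definition. It rests on the text of section 11.2 alone: d) is necessary, both consequences depend on it, and a subject meeting a) to c) with another possible explanation falls outside both. The contrast with the renal criterion and with the protocol's general causality standard suggests that the restriction serves no stated purpose as an alert rule.

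The size is the unknown share q. With an assumed r of 0.5% and the planned 336 subjects, the chance of at least one liver notice falls from 81% to between 72% (q = 25%) and 16% (q = 90%). These figures show sensitivity only and are not estimates for this trial. The conclusion is that d) may delay or suppress the special-interest notice and reduce the count. It does not extend to saying that the notice cannot be given promptly, or that hepatic events go unseen. This is a cheap and worthwhile improvement, not a flaw that undermines the study.

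**What to change.** This concerns reporting only; no dosing or stopping rule is involved.

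1. In Protocol 11.2(2), let a), b) and c) together trigger the immediate notice and define the cases the sponsor counts. State whether the three values must come from the same sample.
2. Take d) out of the trigger and record it afterwards as a causality classification: met, not met or undetermined.
3. Add one table to SAP section 14.2, on the safety set and by arm: subjects meeting a) to c), and how many of those are later classified as meeting d). Use both the local Day 1 to Day 5 values and the central values, since both are already collected. If the database is locked, identify the table as an added analysis, as Protocol 13.4 requires.

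The cost is a sentence or two of protocol text, one table, and a few notices later attributed to another cause. Because recruitment stopped early, item 3 and any reuse of the definition in a later protocol carry most of the remaining benefit.

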11.3 Pregnancy reporting

If the investigator becomes aware that an embryo or fetus of a female subject may have been exposed to investigational product from the day of informed consent to the day after the completion of investigational product therapy, the investigator will immediately report it to the sponsor using the form designated by the sponsor (Attachment 8: Pregnancy Report). If the female subject wishes to give birth, the investigator will follow up until delivery as much as possible to investigate whether there is any effect of investigational product on the newborn, and report the details of the investigation to the sponsor using the pregnancy report form in Appendix 8.

11.4 Contact with the subject's other physicians

The investigator will determine whether any medical encounters outside of this study are being performed by the subject during the study. If the subject is being treated by another physician, the physician will be notified of the subject's participation in the study with the subject's consent. In addition, the investigator (subinvestigator) or a study collaborator will provide subjects with the study participation card, etc. and instruct subjects to present it when they visit other hospitals or departments in order to inform other physicians about subjects' participation in the study through subjects.

12. Subject Discontinuation Criteria and Procedures

